#### 10.5.1. Time Commitment:

- Total time for the coordinator is approximately 2.25 hours for all participants;
- Total time for the patients is approximately 1.25 hour for the 12-month follow-up

### 10.6. Intervention

For patient safety and generalizability, participants in both the control and intervention arms will continue to receive standard medical care from their usual providers. We chose UC only for our control group because pragmatic RCTs are most useful in testing interventions in real-world settings and addressing the question “how does the intervention compare to what we are doing now?”. The study is also designed not interfere with ongoing patient care. To control for changes in medical practice and secular trends and to protect external validity, no participant will be restricted from seeking weight loss treatment once enrolled.

### **10.6.1. Theoretical Basis**

The self-directed lifestyle intervention approach is grounded in Social Cognitive Theory and uses time-tested self-regulation strategies (goal setting, self-monitoring, action planning, and problem-solving) to achieve and maintain realistic intervention goals: 5-10% of baseline weight and at least 150 minutes per week of moderate-intensity physical activity. It stresses a triadic, reciprocally deterministic relationship between the individual, environment, and behavior, and it recognizes that self-efficacy is enhanced through social support and gradual mastery of self-regulation skills. Further, it builds on the premise that long-term changes in diet and exercise and sustained motivation to maintain behavior changes are most likely to occur when the strategies used to motivate and support behavior change are flexible, sensitive to cultural and individual differences, and broadly acceptable to those in the target population. The program promotes the following goals.

### **10.6.2. Evidence-based Intervention Goals**

*Weight:* The intervention is designed to achieve and maintain a weight loss of 5-10% of baseline body weight in a gradual stepwise fashion. This amount of weight loss is safe, feasible and associated with clinically significant reductions in the risk of diabetes and CVRFs. To help achieve and maintain the weight goal, participants are advised to reduce their calorie intake by 500-1000 kcal/day, as recommended in adult obesity guidelines. Participants will gradually achieve the calorie goals through portion control, choices of low-energy nutrient-dense meals and snacks (e.g., whole fruit, vegetables, whole grains, and low-fat, unsweetened dairy products), reduced consumption of refined and/or added carbohydrates/sugars, healthy food preparation techniques, and careful selection of restaurant items.

*Physical Activity:* The physical activity goal is to achieve and maintain a minimum of 150 minutes per week of moderate-intensity physical activity (such as brisk walking). This goal is consistent with the 2008 Physical Activity Guidelines for Americans, and is deemed safe and attainable for most adults, including those with chronic conditions such as COPD. Participants will gradually and steadily increase daily walking with a goal of achieving 150 minutes of brisk walking per week by the end of the 12-week DVD program. They may also choose to adopt regular activities of moderate intensity other than brisk walking. After attaining the minimum goal of 150 minutes per week, participants may choose to be more active; or if participants reach the 150-minute goal but are not achieving the weight goal, they should further gradually increase to 60 minutes/day of moderate physical activity.

### **10.6.3. Intervention Format, Structure, and Content**

There is a national call for the provision and coverage of multicomponent lifestyle interventions for obesity in primary care settings. The challenge historically with such interventions is that they are often too intensive to implement in the real world. The Centers for Medicare and Medicaid Services (CMS) reimbursement policy promotes brief (15 minutes), lower-intensity (compared with efficacy studies), face-to-face behavioral counseling within a limited timeframe (i.e., 6-12 months). The E-LITE interventions, upon which INSIGHT COPD is modeled, fit this general pragmatic framework with likely better efficiency due to use of technology. The INSIGHT COPD trial will contribute to the evidence base needed to inform and guide policy change, in the context of growing interest and evidence in technology-based interventions.

INSIGHT COPD consists of a 12-month intervention that will have 2 distinct stages: core curriculum (months 1-3) and post core (months 4-12). The core curriculum will be delivered using the GLB DVD or on-line viewing option, with supplementary remote lifestyle coaching at the participant’s discretion. The intervention orientation is described in Section 9.3.1. The coach will contact intervention participants within two weeks of randomization for phone orientation, to review the coach role in the intervention, and describe how participants may request coaching if desired. Also, the coach will send biweekly standardized messages via MyFitnessPal as reminders and/or to reinforce the lifestyle change recommendations in the videos.

The lifestyle coach will monitor intervention adherence by downloading participants' self-monitored data from MyFitnessPal and Fitbit web and mobile technologies. For participants who do not use these tools, they will be instructed to mail their booklets every month. The coach will also document the number and content of contacts with participants in a REDCap database.

The main objective of the core stage is to facilitate gradual weight loss through progressive healthful changes in diet quality and physical activity and behavioral skills training. The post core stage is focused on continued gradual weight loss as well as maintenance through participants' self-directed continued dietary and activity changes, and implementation of self-regulation skills through an iterative self-guided mastery process. The intervention components of the core curriculum stage include:

- the 12-session GLB-DVD or on-line session;
- goal setting and self-monitoring via the MyFitnessPal web and mobile technologies (to include: [www.MyFitnessPal.com](http://www.MyFitnessPal.com));
- use of the Fitbit activity tracker and Fitbit.com web and mobile technologies;
- use of a weight scale;
- lifestyle coaching, available at patient request, by phone or by MyFitnessPal secure messaging. Option for personalized lifestyle coaching will continue throughout the post core stage. Lifestyle coaches in [name] team will be available by phone or by secure messaging that is embedded in the free MyFitnessPal web and mobile technologies.

Self-monitoring is key to success in behavioral weight-loss interventions. E-LITE results supported a hypothesized positive relationship between the frequency of self-monitoring on Heart360 and the amount of weight loss. At the start of the intervention, sites will provide each participant in the treatment arm with a Fitbit activity tracker and a standard bathroom weight scale. Participants will be strongly encouraged to self-monitor diet, activity, weight, and session completion through MyFitnessPal and the Fitbit throughout, and beyond the 12-month intervention. Participants will also connect their Fitbit device with their Fitbit.com account, which enables synchronized transfer of their Fitbit daily steps. These features greatly enhance the intervention's reach and adoption potential given that use of the internet and mobile technology is ubiquitous in the U.S.

### 10.7. Payments/Remuneration

Recommended study participant remuneration (depending on local IRB requirements) is \$40 for completing the baseline visit and being randomized. For randomized participants, the recommended remuneration is \$110 for completing the 12-month follow-up. Table 9 summarizes recommended participant payments. Control patients will receive a Fitbit and the end of the 12-month visit. Because of the June 2018 protocol change eliminating the 18-month visit, sites should ask participants who have already completed the 12-month visit to return to complete spirometry, receive a Fitbit if they were in the control group, and receive final remuneration.

**Table 9: Recommended participant payments**

	Baseline, randomized	12-month
Screen fail	--	--
Randomized, either group	\$40	\$110

## 11.0. MEASUREMENTS

Table 10 summarizes measurement and timing of data collection:

Table 10: Timing of measurements and data collection			
	Source	Baseline	12-month
Primary outcome			
Six-minute walk distance	Measured	x	x
Secondary outcomes			
Weight	Measured	x	x
Modified Borg Dyspnea scale	Questionnaire	x	x
12-Item Short Form (SF-12v2)	Questionnaire	x	x
St. George's Respiratory Questionnaire-C	Questionnaire	x	x
CVD risk			
Framingham Risk Score	Measured/ Calculated	x	x
Waist circumference	Measured	x	x
Blood pressure	Measured	x	x
BMI	Calculated	x	x
Other measures			
Height	Measured	x	
Leg fatigue	Questionnaire		
Spirometry	Measured	x	x
Health inventory checklist	Questionnaire	x	x
Medications	Questionnaire	x	x
Health care utilization	Questionnaire	x	x
Demographics	Questionnaire	x	
Intervention: self-monitoring; coach communications	MyFitnessPal; Keeping Track Booklets; REDCap	Throughout 12-month intervention period	

### 11.1. Anthropometric measures

Height, weight, and waist circumference, are measured with participants wearing light indoor clothes without shoes, using a stadiometer, digital or balance beam scale, and tape measure, respectively. We will use standardized protocols published by the *PhenX Toolkit* and the *National Health and Nutrition Examination Survey (NHANES) Anthropometry Procedures Manual*. BMI will be calculated.

### 11.2. Exercise tolerance

Exercise tolerance is assessed with the 6MWT, a widely used assessment of functional exercise capacity in subjects with COPD. The test has been shown to be reliable, safe and valid for measuring functional status in COPD. A coordinator will measure how far an individual can walk in six minutes breathing room air using ATS guidelines. Participants that use walking aids will use them while completing the 6MWT. Participants that use supplemental oxygen are allowed to use supplemental oxygen during the 6MWT.

### 11.3. Spirometry

Lung function is assessed with spirometry which is considered the gold standard for assigning the diagnosis of COPD. We will conduct the testing according to the American Thoracic Society (ATS) recommendations, and ask participants to refrain from taking inhaled medications for breathing during the six hours prior to their visit, unless they are having trouble with their breathing. Spirometry is a routine clinical measure that requires the patient to blow forcefully into a tube for at least six seconds for three-to-eight times until three acceptable results show repeatability. Coordinators will administer this test both before and after the participant inhales a bronchodilator, and measure forced vital capacity (FVC) and forced expiratory volume in one second (FEV1).

These measurements will allow us to determine the presence of COPD by calculating the FEV1/FVC and FEV1 percent predicted using each subject's age, height, weight, and ethnicity. Participants are eligible to participate in INSIGHT COPD if their FEV1/FVC is less than 0.70 and FEV1% predicted >30.

#### 11.4. **Dyspnea and fatigue**

Modified Medical Research Council (mMRC) dyspnea score: Used to assess study eligibility. The mMRC asks patients to recall the degree to which every-day activities elicit dyspnea, scored on a 5-point scale with higher scores indicating greater dyspnea. Participants are eligible to participate in INSIGHT COPD if they score 1 or higher ("I get short of breath when hurrying on the level or walking up a slight hill").

Modified Borg Scale: Used to assess dyspnea and leg fatigue level before and after the 6MWT. This scale assesses symptoms at the time of exercise and does not require patient recall. Scores on the modified scale range from 0 (nothing at all) to 10 (very, very severe).

#### 11.5. **Cardiovascular risk factors (CVR)**

CVR is assessed by waist circumference, the Framingham Risk Score (FRS), blood pressure and BMI. The INSIGHT COPD trial will use the FRS non-laboratory predictors to estimate participants' 10-year risk of myocardial infarction and coronary mortality using age, BMI, systolic blood pressure, smoking status, presence of diabetes assessed by self-report diabetes diagnosis or use of diabetes medication, and self-report use of medication for high blood pressure.

#### 11.6. **Vital signs**

Pulse: Measured in conjunction with the 6MWT according to standardized procedures.

Blood pressure (BP): Measured in conjunction with the 6MWT and used as part of the FRS. Measured using an automatic or manual blood pressure cuff that meets the recommendations of the American Heart Association.

Blood oxygen saturation (SpO2): Measured with an oximeter in conjunction with the 6MWT using standardized procedures.

#### 11.7. **Self-administered instruments**

Demographic and health inventory: Sites ask participants about their socio-demographic characteristics, health behaviors (e.g., smoking, use of personal trainer), comorbid conditions, family history of lung disease, respiratory symptoms, supplemental oxygen, sleep disturbance, COPD exacerbations, medications, and health care utilization.

Generic HRQoL: Assessed using the 12-Item Short form Health Survey (SF-12v2), which is well validated and has physical and mental health component scores.

COPD symptom QoL: Assessed using the St George's Respiratory Questionnaire-C (SGRQ-C). The SGRQ-C, specifically for COPD patients, is a 40-item survey designed to measure health status for chronic airflow limitation. It has two parts that produce Symptom scores and Activity and Impacts scores, as well as a Total score. The SGRQ-C was derived from the original version following detailed analysis of data from large studies in COPD. The intention was to remove the items with the weakest measurement properties in the original instrument, but at the same time ensure that its scores were directly comparable with the original SGRQ.

#### 11.8. **Additional Process Measures**

Data on the proportion and representativeness of patients willing to participate, as well as reasons for declining to participate, are used to assess the potential reach and the likelihood of adoption of the INSIGHT COPD intervention.

## 12.0. SAFETY

This trial has minimal risk, as demonstrated by the excellent safety data in E-LITE. To ensure unbiased determination across treatment arms, the PLG will train clinical center staff to systematically query participants about possible adverse events (AEs) and serious AEs (SAEs) at each scheduled data collection time-point using a body system-based approach. A clinical site clinician (MD, nurse, or other appropriately qualified personnel) will perform safety monitoring based on the AE query forms completed by their center staff, and then make a determination regarding event seriousness, expectedness, and study relatedness. Events rated as serious and unexpected are reviewed by a PTC medical monitor. Sites will report events to their local IRB, the NEMO, Data Safety and Monitoring Board (DSMB), and/or the NHLBI according to all timelines required by these entities.

The PLG will summarize on a semi-annual basis the number of AEs and SAEs for each unidentified treatment group as specified by the NEMO DSMB.

**AEs and SAEs will be reported to the IRB, DSMB, and Sponsor.** Summaries will also be included in the annual progress reports to the sponsor. At the discretion of the DSMB, the Chair may request unblinded results in order to determine the nature and extent of effect of the experimental intervention. Should the DSMB make this request, it will be fulfilled following a procedure which will maintain blinding of the investigators and the staff involved in follow-up data collection and analysis. If, at any time, the investigators believe they are seeing an unexpected increase in SAEs or in AEs that are a cause for concern, this will be specifically brought to the attention of the DSMB and their advice will be sought.

Sites will also follow and comply with their own local institution's adverse event reporting requirements. These reporting requirements may be more stringent than those adopted by INSIGHT COPD. Regardless of what INSIGHT COPD requires, each site must comply with their local IRB's requirements. Depending on the local requirements, a site may report events locally that are not reported to INSIGHT COPD.

**Stopping rules.** Given that the follow-up period is are 12-months, and that the intervention is considered feasible for not only healthy adults, but also older adults and adults with chronic conditions or functional limitations, formal stopping rules for safety, efficacy, and futility are not proposed. Interim monitoring of study outcomes for evidence of efficacy or futility is not planned. Evidence of extremely low rates of patient accrual, extremely high rates of patient drop-out, and/or a marked preponderance in the rates of SAEs in the either study arm will trigger further consideration of both statistical and clinical evidence by the DSMB to decide whether the trial should continue. The DSMB will carefully weigh the risk of completing the trial as planned against the risk of prematurely stopping the trial for safety or futility.

**DSMB recommendations.** At the end of each meeting, DSMB members will make a recommendation regarding the continuation of the trial and the date and format of the next meeting. In addition, there will be an evaluative statement regarding AE/SAEs, protocol exceptions, and other matters of data quality, integrity of the trial, and timeliness. The DSMB's findings and recommendations will be documented in the meeting minutes and transmitted to the Investigators for their information and action. They also will be incorporated into the annual Progress Reports to the sponsor.

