## 10.0. STUDY DESIGN

INSIGHT COPD is a simple, two-arm PCT in which approximately 680 overweight and obese COPD patients, aged 40 years and older, will be randomized to UC or UC plus the self-directed lifestyle intervention for 12 months. Follow-up assessment will occur at 12 months (Figure 4). We hypothesize that intervention participants will have better exercise tolerance at 12 months.

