### 10.5. Follow-up Visit and Data Collection

Participants complete a follow-up visit at 12 months post enrollment. The target time window for completion is +/-2 weeks of the index post-randomization date; however, events outside the influence of the site may prevent this; therefore, it is acceptable to conduct the visit within +/-4 weeks. Visits that occur outside of the acceptable window must be accompanied by justification. Acceptable reasons include participant illness, or inability to reach the participant, participant not able to travel to the site, or suspended visits because of the COVID-19 pandemic. The site is expected to schedule and complete a follow-up site whenever possible even if it falls outside the acceptable window. The staff person conducting these assessments must be different from the person who conducted and oriented the participant to the randomization assignment. The coordinator will assess the measures summarized in Table 8.

Table 8: 12-month measures	
Assessment/activity	Measure
Weight	Measure weight
Vitals	
 
• Blood oxygen saturation level (SpO2)
 
• Resting heart rate
 

Exercise tolerance	
 
• 6MWT distance
 
• Modified Borg dyspnea and leg fatigue rating pre and post 6MWT
 

CVDR	
 
• Waist Circumference
 
• Framingham Risk Score:               
 
○ age
 
○ gender
 
○ smoking status
 
○ systolic BP
 
○ self-report use of BP medication
 
○ self-report diagnosis of diabetes
 
○ self-report use of diabetic or hypoglycemic medication
 
○ BMI
 
 
 
• Blood pressure
 

Self-report surveys	
 
• General health status (SF-12v2)
 
• Health inventory checklist
 
• Medications
 
• Health care utilization
 
• COPD symptoms (SGRQ-C)
 

Spirometry	Measure pre and post bronchodilator: 
 
• FEV1/FVC
 
• FEV1
 
• FVC
 

Intervention adherence	
 
• Self-report DVD viewing: number of sessions viewed self-tracked by participants via MyFitnessPal or paper booklets)
 

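### The only systematic AE/SAE query described after randomisation is at the 12-month visit, so events are solicited once, by year-long recall, and non-attenders are not systematically queried at all

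*Combined protocol and SAP*

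**What the plan says.** Section 12.0 (Safety) aims at unbiased determination across arms by training staff to "systematically query participants about possible adverse events (AEs) and serious AEs (SAEs) at each scheduled data collection time-point", using a body-system approach. A site clinician "will perform safety monitoring based on the AE query forms completed by their center staff". The leadership group is to "summarize on a semi-annual basis the number of AEs and SAEs for each unidentified treatment group as specified by the NEMO DSMB".

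Under Stopping rules in the same section, "formal stopping rules for safety, efficacy, and futility are not proposed". Among the triggers left for DSMB review, "a marked preponderance in the rates of SAEs in the either study arm will trigger further consideration".

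On timing, section 10.0 says "Follow-up assessment will occur at 12 months" and section 10.5 says "Participants complete a follow-up visit at 12 months post enrollment". Table 10 (section 11.0) has two columns, baseline and 12 months. Its only continuous row is intervention self-monitoring and coach communication. Neither Table 8 nor Table 10 has an AE row.

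Section 13.0 requires a telephone contact with every participant four to eight months after randomisation, described as a courtesy and a reminder of the 12-month visit. Its strategies table also asks for contact at least every four months, a secondary contact where appropriate, and efforts to re-engage inactive participants. None of these is given an AE purpose.

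**The concern.** Baseline measures are completed before randomisation (section 10.3), so the commitment to query at every scheduled data collection point yields one post-randomisation query per participant. Three consequences follow.

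- **Late and recalled.** An attender's event in month 1 is first solicited about 11 months later. The health inventory also asks about exacerbations and health care use (section 11.7), but at the same visit.
- **Incomplete.** Someone who misses month 12 gets no systematic query, and no substitute is described for AEs or SAEs. Illness and inability to travel are among the accepted reasons for out-of-window visits (section 10.5). Missing the visit could therefore be related to having had an event.
- **Unequal opportunity to report.** Only the intervention arm has a coach orientation call, biweekly messages and optional coaching (sections 10.3.1 and 10.6.3). No AE query is attached to these contacts, but they give one arm more occasions to mention an event.

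This matters because the DSMB's safety trigger is a judgement about SAE rates by arm, with no formal rule behind it. It is only as good as the ascertainment that feeds it.

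**Working it through.** **Inputs from the documents.** 680 participants, 340 per arm, d = 0.28, 90% power, two-sided alpha 0.05, at least 80% retention (section 14.1); 1:1 allocation (section 10.3); one follow-up visit at 12 months, acceptable within 4 weeks either side (section 10.5); a call at 4 to 8 months (section 13.0); semi-annual summaries (section 12.0).

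**Assumptions, not in the documents.** Events spread evenly over the year; the proportion reached by the call; the event rate in non-attenders relative to attenders.

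**1. The plan's own figure.** d = 0.28 at 90% power needs 269 evaluable per arm (Table 11: 268). Dividing by 0.80 gives 337 (Table 11: 336; planned: 340). With 0.80 × 340 = 272 evaluable, power is 0.904. The 20% attrition allowance is thus the plan's own figure. (Table 11's two sample-size column labels look transposed; this does not affect the point.)

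**2. Participants with no systematic query.** Taking non-retention as a missed 12-month visit: (1 − 0.80) × 680 = 136, or 68 per arm. At an illustrative 90% retention it is 0.10 × 680 = 68.

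**3. Wait from event to query, for attenders.** One query at month 12: mean 12²/24 = 6.0 months, longest 12, and 6/12 = 50% of events lie more than 6 months back. For visits at 11 to 13 months the mean is 5.5 to 6.5 and the share 45% to 54%. With queries at month c and month 12, the mean is [c² + (12 − c)²]/24:

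| Call at month c | Mean wait (months) | Longest wait (months) | Events more than 6 months back |
|---|---|---|---|
| none | 6.0 | 12 | 50% |
| 4 | 3.33 | 8 | 17% |
| 5 | 3.08 | 7 | 8% |
| 6 | 3.00 | 6 | 0% |
| 7 | 3.08 | 7 | 8% |
| 8 | 3.33 | 8 | 17% |

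The rows with a call apply to people whom the call reaches.

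**4. Never queried once the call carries the query.** Assume 80% call reach and 80% attendance. If missing one is independent of missing the other, 0.2 × 0.2 × 680 = 27. If the same people miss both, 0.2 × 680 = 136. The call alone may therefore not help non-attenders.

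**5. Share of events never solicited.** With 20% non-attendance and event-rate ratio r (non-attenders to attenders), the share is 0.2r/(0.2r + 0.8): 20% for r = 1, 33% for r = 2, 43% for r = 3.

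**6. Summaries before a participant's first query.** 12/6 = 2.

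**7. Who could still benefit from the call change.** 28 January 2021 minus 8 months is 28 May 2020. Anyone randomised before then was past the call window when this version was issued.

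**The case against.** The strongest reply is that events can become known well before month 12. Section 12.0 has sites report events on the timelines set by the IRB, NEMO, DSMB and NHLBI, and has investigators alert the DSMB whenever they see a worrying increase. A reader might infer from a single query that the DSMB sees nothing for a year, but the documents do not support that. The 6.0 months is a wait to solicitation, not to detection. With staggered entry, each summary also holds data from participants already queried. What remains is that these clauses govern events a site already knows about. They do not say how a site learns of them.

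A reader might also infer that the between-arm comparison is biased. Year-long recall and missed visits affect both arms through the same query. The only asymmetry the documents show is coach contact, which makes differential unsolicited reporting possible but does not demonstrate it.

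The retention table allows a shortened 12-month visit for primary outcome data, and a reader might infer that the AE query is then lost. Section 12.0 already requires the query at that time-point and exempts no visit.

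Secondary contacts, re-engagement efforts and the section 14.4 commitment to document reasons for missing data could bring a death or serious illness to light. That is so, but none is assigned that task.

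The protocol also argues that risk is minimal, citing E-LITE and earlier diabetes-prevention work, so light monitoring is proportionate. That argues against an elaborate system, not against using an existing form on an existing call. E-LITE enrolled adults with prediabetes or metabolic syndrome (section 8.0), and section 7.0 calls this the first experimental study of its kind in COPD.

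Finally, section 10.2 refers specific procedures to a Manual of Operations, which was not available. It may already contain the query. This objection cannot be answered from the documents.

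**Conclusion.** The point holds as a reading of the protocol as written: one systematic query after randomisation, none for those who miss it, and unequal opportunities for unsolicited reporting in between. At the planned minimum retention up to 136 of 680 would not be systematically queried, and more if retention fell lower. Attenders would wait a mean of 6.0 months to be asked, against 3.0 to 3.3 for those reached by a call that carries the query. The waits rest on even event timing. The effect on non-attenders depends on call reach and its overlap with non-attendance, which the documents do not give.

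The harm shown is late and incomplete ascertainment. A demonstrated bias between arms, or a year of DSMB blindness, is not shown. This is a cheap improvement to safety data, and it does not bear on the primary analysis. Confidence is medium because of the unseen Manual.

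**What to change.** 1. In sections 12.0 and 13.0, attach the existing body-system AE/SAE query, in identical words for both arms, to the call already required at four to eight months. The caller should not assess 12-month outcomes. Sites already need a second person, since section 10.5 says: "The staff person conducting these assessments must be different from the person who conducted and oriented the participant to the randomization assignment".
2. For participants who miss month 12, state that deaths and hospitalisations will be sought through the secondary contacts and re-engagement efforts already in section 13.0. Use the medical record as well, where consent and HIPAA authorisation are confirmed to cover it. The consent item in section 10.1.1 is worded generally, while section 10.2.4.2 names eligibility, supplementing outcomes and data sharing, not safety. The record check therefore cannot be assumed to reach every non-attender.
3. If the Manual of Operations already contains such a query, cite it in section 12.0 instead.

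**Cost.** A few minutes per call, one more use of an existing form, record review for at most about 136 people at planned retention, and a short amendment. An AE conversation may hint at allocation to the caller, hence the separation from outcome assessment. No stopping rule is asked for.

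**Limit.** Under the January 2021 version the call change helps only participants not yet past month 8, that is, randomised after about 28 May 2020. It helps nobody if enrolment had closed by then. Item 2 does not depend on that date.
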